#### **7.1.4 Handling of missing values/censoring/discontinuations**

All missing GGT values will be considered missing at random. No imputation or adjustment to the primary analysis will be done.

#### **7.1.5 Model checking procedures**

Residual plots will be produced and presented within the SAS OUTPUT listing. Residual plots will be checked and data transformations will be applied if necessary.

In the case of convergence issues of the primary model, alternative covariance structures will be considered and compared using standard fit statistics (AIC).

#### **7.1.6 Graphical presentation of results**

Arithmetic mean ( $\pm$ SD) of serum GGT levels and key LFT parameters, and fold change from baseline in serum GGT levels and key LFT parameters will be plotted across time.

Adjusted means and 90% CI from the repeated measures analysis of fold change from baseline in serum GGT levels and key LFT parameters will be plotted across time.

Placebo adjusted fold change from baseline and 90% CI will be plotted across time.

#### **7.1.7 Supportive analyses**

If it turns out that the primary analysis cannot be fitted because data cannot support a saturated model, a simpler covariance matrix such as the compound symmetric covariance structure may be fitted.

## **7.2 Secondary objectives**

### **7.2.1 Variables**

The secondary efficacy/PD variables are the PBC-40 total score, the PBC-40 itch domain subscore, and the VAS scale PRO as well as ALP (alkaline phosphatase).

The change from baseline will be calculated as the difference between each of the post-dose values and the baseline value.

Baseline will be latest available pre-dose measurement.

### **7.2.2 Descriptive analyses**

See section 7.1.2.

### **7.2.3 Statistical model, assumptions and hypotheses**

The difference between each LJN452 dose and placebo will be assessed by Wilcoxon rank sum test for change from baseline in total PBC score and itch subdomain subscore at each visit. A two-sided p-value and 90% CI for each treatment difference will be reported with no adjustment for multiplicity. In addition, summary statistics (mean, median, SD, minimum, maximum) will be reported at each applicable time point.

As an additional secondary end point, a 100mm visual analogue scale (VAS) will be used to assess the severity of patients' itch as well as loss of sleep. The score (distance from left) on the VAS will be recorded for both parameters by the patient marking with a line. The distance marked will be converted to a score between 0 and 10.

The change from baseline in VAS scores for itch and sleep loss will be analyzed by repeated measures analysis of covariance. The model will include treatment as a fixed effect, time as a repeated effect, the treatment by time interaction, the visit by baseline interaction and baseline as a continuous covariate. An unstructured covariance matrix will be used. Two-sided 90% confidence intervals for the difference between each LJN452 dose and placebo will be presented for each visit. The UDCA and pruritus stratification factor will also be included as a fixed effect in the model for the Part 2 analysis. Missing values will not be imputed.

ALP data will be analyzed using the same approach as described in Section 7.1.3.

Additionally, the number and percentage of subjects who have  $ALP < 1.67 \times ULN$  with  $> 15\%$  reduction from baseline and a normal total bilirubin level will be tabulated by part, treatment and visit.

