11.5 Analysis of secondary [REDACTED] variables

11.5.1 Efficacy / Pharmacodynamics

The secondary efficacy/PD variables are the PBC-40 total score, the PBC-40 itch domain subscore, and the VAS scale PRO as well as ALP.

The difference between LJN452 and placebo will be assessed by Wilcoxon rank sum test for change from baseline in total PBC score and itch subdomain score at each visit. A two-sided p-value for a treatment difference will be reported with no adjustment for multiplicity. In addition, summary statistics (mean median std min max) will be reported at each applicable time point.

As an additional secondary end point, a 100 mm visual analogue scale (VAS) will be used to assess the severity of patients itch as well as loss of sleep. The score (distance from left) on the VAS will be recorded for both parameters by the patient marking with a line. The distance marked will be converted to a score between 0 and 10.

The change from baseline VAS scores for itch and sleep loss will be analyzed by analysis of covariance with a baseline covariate, a fixed effect for treatment, visit, and treatment by visit interaction as well as visit by baseline interaction. An unstructured covariance matrix will be used 90% two-sided confidence intervals for the difference between each LJN452 dose and placebo will be presented. The UDCA and pruritus stratification factor will also be included as a fixed effect in the model for Part 2 analysis.

ALP data will be analyzed using the same approach as described in [Section 11.4.2](#). Additionally the number and percentage of subjects who have $ALP < 1.67 \times ULN$ with $> 15\%$ reduction from baseline and a normal total bilirubin level will be tabulated by part, treatment and visit.

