## **7 Statistical methods for Pharmacodynamic (PD) parameters**

Analysis will be done for Part 1 and Part 2 separately unless specifically mentioned.

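### PBC-40 total and itch change are tested without baseline or strata, unlike GGT, ALP and VAS: keep the valid Wilcoxon test and add the VAS model beside it

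*SAP*

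**What the plan says.** For PBC-40, SAP 7.2.3 reads: "The difference between each LJN452 dose and placebo will be assessed by Wilcoxon rank sum test for change from baseline in total PBC score". The itch domain is handled the same way, visit by visit. Protocol 11.5.1 agrees: "The difference between LJN452 and placebo will be assessed by Wilcoxon rank sum test for change from baseline in total PBC score". SAP 7.2.1 defines the variable: "The change from baseline will be calculated as the difference between each of the post-dose values and the baseline value". That subtraction is the only use of baseline, and no stratum enters.

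The other variables are treated differently. In SAP 7.2.3 the repeated-measures model for VAS itch and sleep contains "the visit by baseline interaction and baseline as a continuous covariate", and then: "The UDCA and pruritus stratification factor will also be included as a fixed effect in the model for the Part 2 analysis". ALP is sent to SAP 7.1.3, where the GGT model has the same structure on the log scale. PBC-40 is thus the exception among the primary and secondary efficacy variables, and no reason is given.

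On reporting, Protocol 11.5.1 says: "A two-sided p-value for a treatment difference will be reported with no adjustment for multiplicity". SAP 7.2.3 says: "A two-sided p-value and 90% CI for each treatment difference will be reported with no adjustment for multiplicity". Neither names the estimator behind an interval that accompanies a rank test.

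Part 2 randomisation is stratified by UDCA use and pruritus severity (Protocol 6.3). Severity is split at a screening PBC-40 score of 7 (Protocol 3.2). With 40 questions scored from 1, a total cannot fall below 40, so the cut must refer to a domain score. It is taken here as itch: 3 questions, range 3 to 15 (Protocol 8.3.2).

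**The concern.** PBC-40 total carries the quality-of-life objective and the itch domain has a secondary objective of its own. A baseline is collected (Protocol Table 8-2 for Part 2; for Part 1 it is implied by the change-from-baseline endpoint). If baseline and follow-up are only moderately correlated, subtracting baseline over-corrects, and conditioning on it gives a tighter comparison. The test also ignores the randomisation strata, one of which comes from the same questionnaire.

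There is a second, smaller reason. The visit-wise test uses only patients seen at that visit, while the VAS model uses all visits under missing at random. After treatment is stopped, the required minimum is concomitant treatments and adverse events (Protocol 7.1), so later PBC-40 scores may be missing.

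At stake is the precision of secondary comparisons, including itch. The Part 2 interim analysis reviews whether the sample size is adequate for itch (SAP 4).

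**Working it through.** **1. Nearest stated figure.** The plan gives no power for PBC-40. Protocol 11.7 gives 81% for ALP with 30 against 20, difference 15%, SD 17.8%, two-sided 5% t-test. SE = 17.8 × sqrt(1/30 + 1/20) = 5.14; noncentrality = 15/5.14 = 2.92; df = 48; power = 81.6%. This reproduces, and the same 30 against 20 is used below.

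**2. Theory, unbounded score.** Assume equal SDs at baseline and follow-up and correlation rho. Var(change) = 2σ²(1 − rho); variance after baseline adjustment = σ²(1 − rho²); ratio adjusted/change = (1 + rho)/2.

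| rho | 0.3 | 0.5 | 0.7 | 0.8 | 0.9 |
|---|---|---|---|---|---|
| (1 + rho)/2 | 0.65 | 0.75 | 0.85 | 0.90 | 0.95 |
| Variance saved | 35% | 25% | 15% | 10% | 5% |
| Change-score CI wider by | 24% | 15% | 8% | 5% | 3% |

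**3. Validity of the Wilcoxon test (simulated nulls).** With strata built from a separate screening score, it rejects 8.9 to 10.3% at nominal 10%. With randomisation stratified on dichotomised baseline itself, it rejects 2.7 to 4.1% at nominal 5%. It is valid, and conservative in the second case.

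**4. Power in Part 2, itch domain.** Single-visit comparison, 30 against 20, two-sided 10%, score limited to 3 to 15. The near-normal score is a rounded N(6, 3.2) clipped to the range; the skewed score is 3 plus a gamma variable (shape 0.8, scale 3.5); the heavy-tailed case has t-distributed follow-up noise on 3 df. All are assumptions. Cells show Wilcoxon / baseline ANCOVA, in percent.

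| Score, effect | rho 0.5 | 0.7 | 0.8 | 0.9 |
|---|---|---|---|---|
| Near-normal, +2 | 67.0 / 75.9 | 83.5 / 87.9 | 93.2 / 95.1 | 99.4 / 99.6 |
| Floor-heavy skew, +2 | 85.7 / 84.4 | 94.7 / 92.5 | 98.7 / 96.6 | 100.0 / 99.6 |
| Heavy-tailed, +1.5 | 63.5 / 69.9 | 82.2 / 79.5 | 90.6 / 86.8 | 99.1 / 96.4 |

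Differences (ANCOVA minus Wilcoxon):

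- Near-normal: +8.9, +4.4, +1.9, +0.2 points. Adding strata and varying the screening correlation gives about 9 to 11 at rho 0.5 and 4 to 6 at 0.7.
- Skewed: −1.3, −2.2, −2.1, −0.4. A repeat run gave 84/95/98/100 against 85/93/97/100.
- Heavy-tailed: +6.4, −2.7, −3.8, −2.7.
- If instead only 30% of treated patients worsen, by 6 points, ANCOVA gains more: from 44.1 / 56.7 to 56.3 / 80.5 over the range of rho.

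**5. Interval width, near-normal case.** Mean 90% width, Hodges-Lehmann / baseline ANCOVA: 2.86 / 2.48 at rho 0.5 (13% narrower), 2.26 / 2.08 at 0.7 (8%), 1.40 / 1.36 at 0.9 (3%).

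**6. PBC-40 total.** N(100, 28) clipped to 40 to 200, effect 0.6 SD, Wilcoxon / baseline-and-strata ANCOVA: 63.7 / 75.6 at rho 0.5, 81.9 / 88.0 at 0.7, 99.8 / 99.9 at 0.9.

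**7. Part 1.** SAP 7 covers both parts: "Analysis will be done for Part 1 and Part 2 separately unless specifically mentioned". Twelve completers at 2:1 (Protocol 11.6) give 8 active and 4 placebo per cohort. Pooled placebo, assumed to apply to PBC-40, is 8, 12 or 20 after 2, 3 or 5 cohorts. Near-normal gain: 5 to 9 points at rho 0.5, 2 to 5 at 0.7, 0 to 3 at 0.8, −1 to +1 at 0.9.

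These runs use a single-visit ANCOVA. They approximate the repeated-measures model proposed below and do not reproduce it.

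**The case against.** The strongest reply is that a rank test is a natural choice for a three-item ordinal sum with a floor, and that treating it differently from a 100 mm VAS is no contradiction. The gain in the near-normal case depends on a shape that the documents do not supply; under plausible skew or heavy tails it vanishes or reverses. This stands, and it is why the Wilcoxon test should stay.

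The endpoint is also secondary and unadjusted for multiplicity, in a study that calls itself exploratory (Protocol 3.5); VAS itch is already adjusted. That stands too and limits the weight of the point. On the interval, SAP 1.1 places programming specifications and output shells in other modules, so the estimator may be named there. Since this module is the methodology document, one sentence here is still reasonable.

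A reader might infer more than the documents support:

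- That the Wilcoxon comparison is invalid. Its level is held or conservative in every null case above.
- That adjustment is a free gain at any correlation short of very high, so the Wilcoxon test should be demoted. With no distribution given, the sign of the gain is not fixed.
- That the interim sample-size review is undermined. The plan does not list its itch parameters, so PBC-40 itch being among them is an inference.
- That protocol and SAP conflict over the interval. The SAP adds detail to the protocol's p-value.

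**Conclusion.** The point holds as a modest improvement to secondary analyses. PBC-40 total and itch domain are compared without conditioning on a baseline already collected or on the Part 2 strata, while GGT, ALP and VAS are adjusted for both. In Part 2, for a roughly normal score, adjustment is worth about 10 power points at rho 0.5, about 4 at 0.7 and almost nothing at 0.9. For a floor-heavy or heavy-tailed score it may be worth nothing or cost up to about 4 points in the cases examined. The benefit therefore depends on both correlation and score shape, and PBC-40 values for neither are given. Type I error is not at issue, and no powered endpoint or stated decision rule changes.

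**What to change.** Keep the Wilcoxon test. In SAP 7.2.3, add for PBC-40 total and itch domain the repeated-measures ANCOVA already written for VAS: treatment, visit, treatment by visit, baseline, baseline by visit and, in Part 2, the UDCA and pruritus strata. Report the adjusted difference between each dose and placebo with a two-sided 90% CI at each visit. State that the 90% CI accompanying the Wilcoxon test is Hodges-Lehmann. Make Protocol 11.5.1 match, including the comparison of each dose with placebo.

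The cost is wording in two documents and one more prespecified analysis per score; no new data or patients are needed. The drawback is a linear mean model for a bounded score. SAP 7.2.4 already provides, by reference to 7.1.5, for residual checks and alternative covariance structures if the model does not converge.

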### **7.2.4 Model checking procedures**

See section 7.1.5.

### **7.2.5 Graphical presentation of results**

Arithmetic mean ( $\pm SD$ ) of the absolute levels and change from baseline in secondary variables will be plotted across time.

Box plots will be provided for change from baseline VAS and PBC scores.

Adjusted means and 90% CI from the repeated measures analysis of change from baseline in VAS scores for itch and sleep will be plotted across time.

Placebo adjusted change from baseline and 90% CI will be plotted across time.

## **8 Statistical methods for safety and tolerability data**

### **8.1.1 Variables**

Adverse events, vital signs (blood pressure, pulse rate, body temperature), ECG intervals, laboratory measurements, as well as subject demographics, baseline characteristics, and treatment information.

### **8.1.2 Descriptive analyses**

#### **Subject demographics and other baseline characteristics**

All data for background and demographic variables will be listed by treatment group and subject. Summary statistics will be provided by treatment group.

Relevant medical history, current medical conditions, results of laboratory screens, drug tests and any other relevant information will be listed by treatment group and subject.

#### **Treatments (study drug, rescue medication, other concomitant therapies, compliance)**

Data for study drug administration (rescue medication) and concomitant therapies will be listed by treatment group and subject.

#### **Vital signs**

All vital signs data will be listed by part, cohort, treatment, subject, and visit/time and if ranges are available abnormalities (and relevant orthostatic changes) will be flagged. Summary statistics will be provided by part, cohort, treatment and visit/time.

#### **ECG evaluations**

All ECG data will be listed by part, cohort, treatment, subject and visit/time, abnormalities will be flagged. Summary statistics will be provided by part, cohort, treatment and visit/time.

#### **Clinical laboratory evaluations**

All laboratory data will be listed by part, cohort, treatment, subject, and visit/time and if normal ranges are available abnormalities will be flagged. A separate listing is provided presenting all parameters in a subject with any abnormal values. Summary statistics will be provided by part, cohort, treatment and visit/time.

The following special clinical laboratory evaluations will be listed and summarized by part, cohort, treatment and visit/time:

- Fasting lipid panel
- Alpha-fetoprotein (Listed only)
- Blood type (Listed only)

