3.6 Risks and benefits

There is no benefit expected for subjects participating in this short-term study.

Preliminary data from study CLJN452X2101 have demonstrated isolated increases in transaminases ALT and AST [REDACTED]. These changes normalized spontaneously have not been observed at the proposed starting dose.

The risk to subjects in this trial will be minimized by adherence to the eligibility criteria, close clinical monitoring, and stopping rules.

A maximum of 500 mL of blood is planned to be collected over a period of 16 weeks, from subjects as part of the study (Part 1 sample volume will be approximately 490 mL and Part 2 will be approximately 450 mL). Additional samples for monitoring of any safety findings may be required, and would be in addition to this volume. This is not considered to be a risk for this population.

There may be unknown risks of LJN452 which may be serious and unforeseen.

4 Population

The study population will be comprised of patients with PBC.

In Part 1, a total of approximately 15 patients will be enrolled in each cohort of the study and randomized.

In Part 2, a total of approximately 88 patients will be enrolled and randomized. Final sample size for Part 2 will be informed by the interim analysis.

The investigator must ensure that all subjects being considered for the study meet the following eligibility criteria. No additional criteria should be applied by the investigator, in order that the study population will be representative of all eligible subjects.

Subject selection is to be established by checking through all eligibility criteria at screening and baseline (for Part 1). A relevant record (e.g., checklist) of the eligibility criteria must be stored with the source documentation at the study site.

Deviation from **any** entry criterion excludes a subject from enrollment into the study.

In Part 1 replacement subjects may be enrolled to replace subjects who discontinue the study for reasons other than safety.

4.1 Inclusion criteria for Parts 1 and 2

Patients eligible for inclusion in this study have to fulfill all of the following criteria:

1. Written informed consent must be obtained before any assessment is performed.
2. Age \geq 18 years
3. Diagnosis of PBC as demonstrated by the presence of at least 2 of the following 3 diagnostic criteria:
 - History of Alkaline Phosphatase elevated above upper limit of normal for at least 6 months

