9.1 Adverse events

An adverse event (AE) is any untoward medical occurrence (i.e., any unfavorable and unintended sign [including abnormal laboratory findings], symptom or disease) in a subject or clinical investigation subject **after providing written informed consent** for participation in the study. Therefore, an AE may or may not be temporally or causally associated with the use of a medicinal (investigational) product.

The occurrence of adverse events should be sought by non-directive questioning of the subject at each visit during the study. Adverse events also may be detected when they are volunteered by the subject during or between visits or through physical examination, laboratory test, or other assessments.

Abnormal laboratory values or test results constitute adverse events only if they fulfill at least one of the following criteria:

- they induce clinical signs or symptoms,
- they are considered clinically significant,
- they require therapy.

Clinically significant abnormal laboratory values or test results should be identified through a review of values outside of normal ranges/clinically notable ranges, significant changes from baseline or the previous visit, or values which are considered to be non-typical in patients with underlying disease. Investigators have the responsibility for managing the safety of individual subject and identifying adverse events. Alert ranges for liver related events are included in [Section 9.3](#).

Adverse events must be recorded on the Adverse Events CRF for subjects that pass screening and enter into the study. The adverse events should be reported according to the signs, symptoms or diagnosis associated with them, and accompanied by the following information:

1. The Common Toxicity Criteria (CTC) AE grade (version 4). If CTC-AE grading does not exist for an adverse event, use:
 - 1=mild,
 - 2=moderate,
 - 3=severe
 - 4=life threatening.CTC-AE grade 5 (death) is not used, but is collected in other CRFs (e.g., Study Completion, Death/Survival).
2. its relationship to the study treatment (no/yes)
3. its duration (start and end dates) or if the event is ongoing an outcome of not recovered/not resolved should be reported.
4. whether it constitutes a serious adverse event (SAE) See [Section 9.2](#) for definition of SAE
5. action taken regarding investigational treatment.

All adverse events should be treated appropriately. Treatment may include one or more of the following:

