11.5.2 Safety

Vital signs

All vital signs data will be listed by part, treatment, subject, and visit/time and if ranges are available abnormalities (and relevant orthostatic changes) will be flagged. Summary statistics will be provided by part, treatment and visit/time.

ECG evaluations

All ECG data will be listed by part, treatment, subject and visit/time, abnormalities will be flagged. Summary statistics will be provided by treatment and visit/time.

Clinical laboratory evaluations

All laboratory data will be listed part, by treatment, subject, and visit/time and if normal ranges are available abnormalities will be flagged. Summary statistics will be provided by treatment and visit/time.

Adverse events

All information obtained on adverse events will be displayed by treatment and subject.

The number and percentage of subjects with adverse events will be tabulated by body system and preferred term with a breakdown by treatment. A subject with multiple adverse events within a body system is only counted once towards the total of this body system.

Other safety evaluations

Not applicable.

Immunogenicity

Not applicable.

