ALT or AST > 3 x ULN and INR > 1.5	
 • Discontinue study drug • Hospitalize, if clinically appropriate • Establish causality and complete liver event checklist (in SOM) 	--	Continue monitoring with Repeat tests ^a until resolution ^c	--	--
ALT or AST > 8 x ULN	
 • Discontinue study drug • Hospitalize if clinically appropriate • Establish causality and complete liver event checklist (in SOM) 	--	Continue monitoring with Repeat tests ^a until resolution ^c	--	--
ALT or AST > 2 X Baseline AND > 3 x ULN AND accompanied by symptoms^b	
 • Discontinue study drug • Hospitalize if clinically appropriate • Establish causality and complete liver event checklist (in SOM) 	--	Continue monitoring Repeat tests ^a until resolution ^c	--	--

Criteria	First Action	Result	Second Action	Result	Third Action
ALT or AST > 2 X Baseline AND > 5 to \leq 8 x ULN	
 Repeat tests^a within 48 hours of notification of result HOLD study drug until repeat test results available Establish causality and complete liver event checklist (in SOM) 	↑	Part 1 
 Discontinue study drug 		
 Continue monitoring with Repeat tests^a 2-3 times per week until resolution ^c Update liver event checklist
			Part 2 
 Reduce dose (Table 6-1). Restart study drug at reduced dose Repeat tests^a 2-3 times a week after re-starting study drug Update liver event checklist (in SOM) 	↑	Part 2 If elevated after re-starting study drug, discontinue study drug 
 Continue monitoring with Repeat tests^a until resolution ^c Update liver event checklist
				↓	If values normalize, continue with reduced dose. 
 Repeat tests^a two and three weeks after re-starting study drug If levels remain \geq 2x Baseline 3 weeks after dose reduction, discontinue study drug 
 Continue monitoring with Repeat tests^a until resolution ^c Update liver event checklist

Criteria	First Action	Result	Second Action	Result	Third Action

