### **Adverse events**

All information obtained on adverse events will be displayed by part, cohort, treatment and subject.

The number and percentage of subjects with adverse events will be tabulated by body system and preferred term with a breakdown by treatment. A subject with multiple adverse events within a body system is only counted once towards the total of this body system and treatment.

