#### **8.1.3 Graphical presentation of results**

Boxplots to visualize trends in longitudinal safety data (vitals, ECG, lab parameter) will be created.

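### No planned laboratory output counts, by arm, the patients who ever cross a Table 15-1 liver limit, so isolated transaminase rises are split across visits and understated in the summary of a primary objective

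*SAP*

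**What the plan says.** Safety and tolerability form a primary objective in both documents (Protocol 2.1, SAP 2.1.1), and Protocol 2.1 names safety laboratory tests among the endpoints.

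The planned laboratory outputs are:

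- **By-arm statistics.** SAP 8.1.2, Clinical laboratory evaluations: "Summary statistics will be provided by part, cohort, treatment and visit/time". Protocol 11.5.2 is similar: "Summary statistics will be provided by treatment and visit/time".
- **Listings.** All values are listed and flagged against normal ranges. In addition, "A separate listing is provided presenting all parameters in a subject with any abnormal values".
- **Graphics.** SAP 8.1.3: "Boxplots to visualize trends in longitudinal safety data (vitals, ECG, lab parameter) will be created".

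The only by-arm safety output that counts patients is the adverse event table: "The number and percentage of subjects with adverse events will be tabulated by body system and preferred term with a breakdown by treatment". Protocol 9.1 limits what reaches it: "Abnormal laboratory values or test results constitute adverse events only if they fulfill at least one of the following criteria". The criteria are clinical signs or symptoms, clinical significance, or a need for therapy. Crossing a Table 15-1 limit is not one of them. SAP 8.1.2 lists study drug administration and does not tabulate it, so it plans no by-arm count of holds, reductions or stops.

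Table 15-1 sets limits for single patients in multiples of ULN and of baseline, each with its own action. For one ALT/AST band the first action includes "HOLD study drug until repeat test results available".

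**The concern.** Protocol 3.6 reports that preliminary data from another study of the compound "have demonstrated isolated increases in transaminases ALT and AST". Part of that text is redacted, and the changes are said to have normalised spontaneously. A signal of this kind lies in a few patients, each for a short time. Statistics by visit describe the bulk of an arm at one time point, so they respond weakly to it.

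Two features of the trial weaken them further. After a rise, Table 15-1 can lead to a hold, a reduction or a stop, so later values in the affected arm partly reflect that management. Repeat tests fall within 48 hours and then two to three times a week after restart, whereas Part 2 visits are at weeks 3, 5, 9 and 13. The SAP does not say how these repeats enter a summary by visit/time.

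The listing of patients with any abnormal value does not fill the gap. Protocol 4.1 requires ALP of at least 1.67 × ULN or bilirubin above ULN, so every eligible patient qualifies with a liver value outside the normal range. The listing will hold nearly everyone and will not separate the arms.

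At stake is a reader seeing similar mean ALT across arms when a material share of one arm crossed a limit. That bears on a primary objective and on dose selection for later development, which Protocol 3.2 names as a use of Part 2.

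**Working it through.** The documents state no rate, effect size or power for laboratory safety, so there is no figure to reproduce. The steps below compare the two kinds of summary.

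**Inputs from the documents.** Part 2 has 33 patients per active arm and 22 on placebo (Protocol 6.2), with four on-treatment visits after baseline (Protocol 3.1).

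**Assumed inputs.** The documents give no transaminase distribution and no rate of crossing limits. The size and number of rises below are illustrations.

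**1. One patient, one visit.** Shift in the visit mean = (peak − usual value) / 33.
- Peak 5 × ULN from 1.5: 3.5 / 33 = 0.11 × ULN (0.09 to 0.12 for usual values of 2 down to 1 × ULN).
- Peak 8 × ULN from 1.5: 6.5 / 33 = 0.20 × ULN (0.18 to 0.21).

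**2. Five patients, one rise each, spread evenly.** Each rises from 1.5 to 6 × ULN, a rise of 4.5, and every peak falls on a visit.
- Patients elevated per visit: 5 / 4 = 1.25.
- Shift in each visit mean: (1.25 / 33) × 4.5 = 0.17 × ULN.
- Per-patient count: 5 / 33 = 15%, exact 95% CI 5.1% to 31.9%.
- For comparison, 0 of 22 on placebo has an exact upper bound of 15.4%.

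**3. Range of rates.** If a share p of 33 patients has one rise each, spread evenly over four visits:

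| p | Patients ever affected (33p) | Average per visit (33p/4) |
|---|---|---|
| 5% | 1.7 | 0.4 |
| 10% | 3.3 | 0.8 |
| 15% | 5.0 | 1.2 |
| 20% | 6.6 | 1.7 |

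Even a count by visit would show a quarter of the per-patient figure.

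**4. Simulation with natural variation.** Assumptions: geometric mean 1.5 × ULN, between-patient log SD 0.4, within-patient log SD 0.15, and 5 of 33 patients with one threefold rise at a random visit.
- Visit mean: 1.64 to 1.77 × ULN.
- Visit median: 1.51 to 1.54 × ULN.
- Patients above 2 × baseline at any visit: 4.9 of 33 (15%). At an average visit: 1.2 of 33 (3.7%).

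**5. The trial's other rules count patients.** The Part 1 cohort stopping rule in Protocol 7.4 counts subjects over ALT/AST or bilirubin limits. SAP 7.2.3 tabulates patients meeting an ALP and bilirubin response threshold. No safety table does the same for liver limits.

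**The case against.** A reader might infer that transaminase peaks are lost from the report, or that only scheduled visits are summarised. The documents support neither reading.

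- The SAP says visit/time and is silent on unscheduled values. Table 8-2 has an unscheduled column that includes liver function tests, and all laboratory data are listed and flagged.
- Table 15-1 repeats follow notification of a result. In a patient without symptoms the triggering value will usually come from a visit draw and enter that visit's statistics. A maximum or a boxplot outlier may show it. The case in which every peak falls between visits and the means do not move at all is therefore unlikely.
- The adverse event table is a partial per-patient count. Investigators are told to look for significant changes from baseline, and many rises that lead to a hold or stop would plausibly be judged clinically significant.
- Patients who stop treatment are not counted as withdrawn and should return where possible (Protocol 7.1). The minimum data set after stopping does not include laboratory tests, so some loss remains possible.
- SAP 7.1.3 allows a repeated-measures analysis of key liver parameters. That too works by visit.
- Table shells and Module 8 (SAP 1.1) and the DMC outputs are separate documents that were not available for this review. They may contain such a table.
- Laboratory safety is descriptive and unpowered. Even in the illustration, 5/33 against 0/22 gives a two-sided Fisher p of about 0.08.

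These points limit the consequence but do not close the gap. A visit maximum does not count patients across visits, capture as an adverse event depends on judgement, and Module 3, which sets the methodology, does not call for a threshold table.

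**Conclusion.** The point holds as a gap in the planned summary. No output specified in the protocol or SAP counts patients per arm who ever meet a Table 15-1 limit, and none gives the worst post-baseline ALT, AST or bilirubin. Isolated rises at different visits are understated in the by-arm summary of a primary objective. They are not removed from the data.

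The size is illustrative only: about 0.17 × ULN per visit mean against 15% of patients, with 5 of 33 affected, rises from 1.5 to 6 × ULN, and an even spread over four visits. The roughly fourfold split follows from four visits and one rise per patient. Longer rises would be split less.

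No stated figure, sample size or test changes. The addition is worth making because it is cheap and concerns a primary objective.

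**What to change.** Add one table to SAP 8.1.2, per part and treatment, giving:

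- **(a)** the maximum post-baseline ALT, AST, total bilirubin and serum creatinine, as multiples of ULN and of baseline, from all results in the database including unscheduled ones;
- **(b)** n (%) of patients ever meeting each Table 15-1 ALT/AST, bilirubin and combined limit, and each serum creatinine limit in Table 15-2.

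Leave out the albumin- and protein-creatinine ratio limits of Table 15-2. Protocol 8.4.4 plans dipstick urinalysis and Table 8-2 schedules no such ratio, so they cannot be counted from routine data.

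Count dose-reduced patients under their original treatment. Make this explicit against Protocol 11.1 and SAP Section 5, which analyse by treatment received and refer to treatment up to the reduction without saying where later safety values belong.

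Reconcile Protocol 6.2.1, which keeps local-laboratory repeat results in source documents only, with Protocol 9.3, which asks for follow-up information to be recorded in the CRF as appropriate. Until then, state that the table rests on results held in the database.

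The cost is SAP wording and one table, possibly incomplete for local-laboratory repeats. The table needs no extra patients, visits or tests and no change to any clinical rule. Reconciling the two protocol sections is a separate wording matter.
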